7.2.1 Pharmacokinetic Profile Assessments

The PK profile of ADCT-301 (total antibody; $DAR \geq 0$), PBD-conjugated antibody ($DAR \geq 1$), and free warhead SG3199 will be assessed.

Additional PK, ADA, cytokines, and sCD25 blood samples will be collected, at the discretion of the Investigator, during any visit where toxicity is observed. A PK, ADA, cytokines, and sCD25 sample will also be collected concurrently with any other blood draw to assess safety (e.g., Unscheduled Visit), if possible. All PK samples will be evaluable as long as the actual collection times are recorded.

The PK profile will include determination of standard PK parameters: C_{max} , T_{max} , area under the concentration-time curve (AUC) from time zero to the last quantifiable concentration (AUC_{0-last}), area under the concentration-time curve from time zero to the end of the dosing interval ($AUC_{0-\tau}$), area under the concentration-time curve from time zero to infinity ($AUC_{0-\infty}$), accumulation index (AI), volume of distribution at steady-state (V_{ss}), mean residence time (MRT), and terminal elimination phase rate constant (λ_z), $t_{1/2}$, C_L , and V_z .

[REDACTED]

7.3 Safety and Tolerability Assessments

Safety will be assessed based on AEs, SAEs, treatment discontinuations due to AEs, DLTs, measurements of cytokines in serum, periodic 12-lead ECG recordings, physical examinations, vital signs measurements, ECOG performance status, and hematology, biochemistry, coagulation panel, pregnancy testing (for women of child-bearing potential) and urinalysis test results. Adverse events will be graded according to CTCAE Version 4.0. A schedule of the safety assessments is provided in [Appendix 13.2 \(Table 6\)](#).

7.3.1 Dose-Limiting Toxicities and Dose-Escalation Scheme

7.3.1.1 Definition of Dose-Limiting Toxicities

A DLT is defined as any of the following events, except those that are clearly due to underlying disease or extraneous causes:

- A hematologic DLT is defined as:
 - Grade 3 or higher event of neutropenia and/or thrombocytopenia or a Grade 4 anemia, with a hypocellular bone marrow lasting for 6 weeks or more after the start of a cycle, in the absence of residual leukemia (i.e., with <5% blasts). In case of a normocellular bone marrow with <5% blasts, 8 weeks with \geq Grade 3 pancytopenia will be considered a DLT.
- A non-hematologic DLT is defined as:
 - Grade 4 tumor lysis syndrome (Grade 3 TLS will not constitute DLT unless it leads to irreversible end-organ damage).
 - Grade 3 or higher AEs (including nausea, vomiting, diarrhea, and electrolyte imbalances lasting more than 48 hours despite optimal therapy; excluding all grades of alopecia).
 - Grade 3 or higher hypersensitivity reaction (regardless of premedication).
 - Grade 3 or higher skin ulceration.
 - Peripheral sensory or motor neuropathy \geq Grade 2.

Note: The DLT observation period for dose-escalation will be 1 cycle. Patients who experience a DLT during Cycle 1 are to be permanently discontinued from the study.

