 - Grade 4 tumor lysis syndrome (Grade 3 TLS will not constitute DLT unless it leads to irreversible end-organ damage).
 - Grade 3 or higher AEs (including nausea, vomiting, diarrhea, and electrolyte imbalances lasting more than 48 hours despite optimal therapy; excluding all grades of alopecia).
 - Grade 3 or higher hypersensitivity reaction (regardless of premedication).
 - Grade 3 or higher skin ulceration.
 - Peripheral sensory or motor neuropathy \geq Grade 2.

The DLT observation period for dose-escalation will be 1 cycle. Patients who experience a DLT during Cycle 1 are to be permanently discontinued from the study.

Investigational Product, Dosage, and Mode of Administration:

ADCT-301 is a sterile formulation containing PBD-conjugated HuMax[®]-TAC (DAR \geq 1), HuMax[®]-TAC (DAR = 0), and SG3249. It is provided pre-formulated in 10-mL glass vials containing approximately 30 mg of ADCT-301 per vial (deliverable volume 5.4 mL at 6 mg/mL). The appropriate quantity of ADCT-301 will be diluted in 50 mL of 5% dextrose in water (D5W).

Patients will receive a 1-hour intravenous (IV) infusion of ADCT-301 on

Day 1 of Cycle 1. If ADCT-301 is well tolerated after the first infusion, the infusion duration may be shortened to 30 minutes for subsequent cycles for that patient, at the Investigator's discretion.

The investigational product administration schedule is as follows:

Every 3-Week Administration

Patients will be given ADCT-301 on Day 1 of each 3-week (21-day) treatment cycle.

Weekly Administration

Patients will be given ADCT-301 (weekly [QW]) on Days 1, 8, and 15 of each 3-week (21-day) treatment cycle.

A patient will maintain the same treatment schedule throughout the duration of the trial.

Once a patient achieves CR/CRi, frequency or dose may be adjusted by the DESC based on emerging safety, efficacy, and PK profile.

The trial will be continuously monitored for emerging safety, efficacy and/or PK profile, and the DESC will determine if it is appropriate to maintain a QW schedule, revert to an every 3-week (Q3W) schedule, or test other dosing regimens.

Dose-Escalation Design:

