4.1.1 Dose-escalation (Part 1) and Determination of Maximum Tolerated Dose

Dose-escalation will be conducted according to a 3+3 design (Figure 2). The initial dose of ADCT-301 will be 3 µg/kg (Dose Level 1), and the highest allowed dose will be 150 µg/kg every three weeks (50 µg/kg every week).

The DLT (see Section 7.3.1.1 for further details) observation period for dose-escalation will be 1 cycle. The first patient at each new dose level must be observed for 7 days for occurrence of AEs prior to treating the second patient at that dose level. Patients will be entered sequentially to each dose level.

For each dose level, if none of the first 3 patients at that level experiences a DLT, new patients may be entered at the next higher dose level. If 1 of 3 patients experiences a DLT, up to 3 more patients are to be treated at that same dose level. If none of the additional 3 patients at that dose level experiences a DLT, new patients may then be entered at the next higher dose level. However, if 1 or more of the additional 3 patients experiences a DLT, then no further patients are to be started at that dose level and the preceding dose is identified as the MTD. The MTD, therefore, is defined as the highest dose level at which none of the first 3 treated patients, or no more than 1 of the first 6 treated patients, experiences a DLT.

No intra-patient dose-escalation is allowed.

[figure not shown]

Figure 2. Schematic Representation for Dose-escalation (3+3) Design

* For every 3 weeks (Q3W) administration, the dose increase will never exceed 100% or 20 µg/kg at dose levels below 100 µg/kg and 50 µg/kg for dose levels between 100 and 150 µg/kg, whichever is less. Dose adjustment for other treatment schedules, such as QW dosing are included below. Abbreviations: DLT, dose-limiting toxicity; MTD, maximum tolerated dose; <, less than; ≥ greater than or equal to.

The number of dose levels will depend on the emergent toxicity profile of ADCT-301 and will be decided by the DESC ([Section 7.3.1.2](#)); PK and PD evaluations may also inform decision making.

During Part 1 (dose-escalation), the DESC may expand enrollment at doses below the current dose level as part of the dose-escalation process. Additional patients may only be added at a lower dose level provided there is at least 1 patient who has achieved a PR or better ([Section 7.1](#)).

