5.1.7.1 Bone Marrow Aspirate or Biopsy

A BMA (or biopsy if aspirate unattainable) will be obtained at the Day 19 visit (± 3 days) of each cycle, beginning with Cycle 2, and repeated at each subsequent cycle, until disease progression, CR (Section 7.1), or CRi is achieved. Once CR/CRi is achieved, sampling will be repeated at least every 3 cycles, or, as clinically indicated.

A bone marrow sample (aspirate or biopsy if aspirate unattainable) will also be collected at the EOT Visit (Section 5.1.8) for those patients who have not demonstrated disease progression and if their most recent sample was obtained more than 12 (± 1) weeks prior to the EOT Visit.

Response to treatment with ADCT-301 (Section 7.1) is to be performed by an approved clinical laboratory.

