6.4 Dose Delays and Modifications

Patients will receive the first 2 cycles, irrespective of blood count recovery. For patients achieving a CR/CRi, the subsequent cycle would be delayed until peripheral blood count recovery (absolute neutrophil count [ANC] $>0.5 \times 10^9/L$ and/or platelets $>50 \times 10^9/L$).

The Investigator should suspend ADCT-301 dosing for up to 21 days for any patient who experiences a protocol-defined DLT during any treatment cycle. At the discretion of the Investigator, the dose may also be delayed for up to 21 days for any toxicity that does not meet DLT criteria. Resumption of dosing with ADCT-301 after suspension is at the discretion of the Investigator, based on assessment of the patient's clinical condition and whether or not the patient is deriving potential clinical benefit from treatment with ADCT-301. Following recovery to CTCAE Grade 1 or to baseline grade, treatment with ADCT-301 may resume at the Investigator's discretion.

Patients who resume treatment following a dose delay may, at the discretion of the Investigator, have their dose reduced by 1 dose level. If toxicity recurs at a severity that would mandate a dose delay, then the dose may be further reduced 1 dose level. If toxicity recurs at such level, then the patient is to be discontinued from treatment. Dose re-escalation is allowed at the Investigator's discretion, at maximum to the dose level the patient was initially assigned to.

Dosing frequency may be adjusted according to individual patient response as described in [Section 4.1.1](#).

Patients experiencing certain types of infection during the course of participation in this clinical study also must delay further dosing, as stipulated in [Section 7.3.4.5](#).

Patients experiencing any autoimmune toxicities (e.g., endocrinopathies) \geq grade 1 need to be followed at least weekly to quickly detect deterioration and modify dosing as per DLT criteria (can be done by telephone unless symptoms worsen).

Patients who experience a DLT ([Section 7.3.1.1](#)) during Cycle 1 are to be permanently withdrawn from the study. Patients who experience the following significant toxicities will be immediately and permanently withdrawn from treatment with ADCT-301:

- Any patient who experiences a CTCAE Grade 3 or higher hypersensitivity reaction, regardless of premedication, during any cycle of treatment ([Appendix 13.2](#)).

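### Hematologic DLTs take 6 or 8 weeks to confirm, the Part 1 DLT window is 21 days, and no rule adds a late-confirmed event to the dose level's 3+3 tally

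*Protocol*

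**What the plan says.** Protocol 7.3.1.1 has two DLT classes. The hematologic class is defined by persistence. Grade 3 or higher neutropenia or thrombocytopenia, or Grade 4 anemia, counts "with a hypocellular bone marrow lasting for 6 weeks or more after the start of a cycle, in the absence of residual leukemia", meaning under 5% blasts. If the marrow is normocellular, also with under 5% blasts, the requirement is 8 weeks of Grade 3 or higher pancytopenia.

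The note closing that section says: "The DLT observation period for dose-escalation will be 1 cycle". The Synopsis fixes the cycle length, with Q3W dosing "on Day 1 of each 3-week (21-day) treatment cycle"; the weekly schedule uses the same 21-day cycle. The DLT-evaluable set in 8.4 is also built on a first cycle of 21 days.

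In 4.1.1, the MTD is the highest dose at which "none of the first 3 treated patients, or no more than 1 of the first 6 treated patients, experiences a DLT". That sentence has no day limit. The same section starts weekly dosing from a Q3W dose at which three patients finished the observation period without a DLT, and it describes doses as cleared by reference to the DLT period. Within a cohort, the first patient "must be observed for 7 days for occurrence of AEs prior to treating the second patient at that dose level".

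On timing, marrow sampling under 5.1.7.1 is at Day 19 (±3 days) of each cycle, "beginning with Cycle 2, and repeated at each subsequent cycle". Under 6.4, "Patients will receive the first 2 cycles, irrespective of blood count recovery"; only after CR or CRi is it stated that "the subsequent cycle would be delayed until peripheral blood count recovery". Section 6.4 also suspends dosing for a DLT in any cycle and permanently withdraws patients whose DLT occurs in Cycle 1.

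SAP 3.3 reports early termination before escalation was complete. SAP 4.8.1 (Dose-limiting Toxicities) specifies a DLT listing and nothing more. SAP 4.2, item 3, counts as an important deviation any patient who met a withdrawal criterion but was not withdrawn, and a Cycle 1 DLT is one of those criteria.

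**The concern.** DLTs and the MTD are Part 1 primary endpoints (8.2.1). If one of the two DLT classes cannot be confirmed inside the window that decides clearance, the 3+3 count runs in practice on non-hematologic events alone, unless late-confirmed events are added back. The text neither adds them back nor says that they are excluded from the MTD. Two careful readers could give the same dose level different tallies.

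The same uncertainty reaches the increment rule in 4.1.1. There, a DLT at a dose level lowers the maximum next step from 100% to 50% (Q3W) or from 50% to 25% (QW), again with no day limit. It also reaches the Cycle 1 withdrawal rule, and through that the deviation count in the SAP.

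**Working it through.** The plan gives no assumed DLT rate and no operating characteristics, so there is no stated figure to reproduce. The check is day arithmetic, then a comparison of the rules, then an illustration.

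**One patient, planned schedule.** Inputs: 6 weeks = 42 days and 8 weeks = 56 days (7.3.1.1); window = 21 days (7.3.1.1, Synopsis, 8.4).
- 6-week limb: 42 − 21 = 21 days after the window closes.
- 8-week limb: 56 − 21 = 35 days after the window closes.
- First on-study marrow, Cycle 2 Day 19: 21 + 19 = Day 40, range 37 to 43.
- Next scheduled marrow if CR/CRi has not been reached, Cycle 3 Day 19: 42 + 19 = Day 61, range 58 to 64. After CR/CRi, 5.1.7.1 requires only one marrow every 3 cycles, or as clinically indicated.
- Doses by Day 42: QW on Days 1, 8, 15, 22, 29 and 36 = 6; Q3W on Days 1 and 22 = 2. By Day 56 without delays: 8 and 3.

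**What is known when a cohort clears.** This depends on accrual.
- Fastest 3-patient cohort: patient 1 on Day 1, patients 2 and 3 on Day 8. The last window ends on 8 + 20 = Day 28. The patients are then at their own Days 28, 21 and 21, which is 14, 21 and 21 days short of Day 42. Neither limb is reached.
- Six-patient cohort, expanded once the first three finish: patients 4 to 6 start on Day 29 and end on 29 + 20 = Day 49. The first three, less any withdrawn for a DLT, are at their own Days 49, 42 and 42, so a 6-week event among them may be known. Patients 4 to 6 are at Day 21.
- Slow accrual: patient 1 reaches Day 42 (or 56) by clearance if the last patient starts at least 21 (or 35) days after the first.

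So a late event can sometimes be known at clearance, but it always lies outside that patient's own window.

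**Rules side by side.**
- 7.3.1.1 and the clearance wording in 4.1.1 point to the 21-day window.
- The MTD sentence in 4.1.1 has no day limit.
- 6.4 recognises DLTs in any cycle, but only for that patient's dosing.
- 7.3.1.2 lets the steering committee (DESC) set dose levels and the MTD from safety findings and DLTs. That is authority to decide, not a counting rule.
- 8.4 says who is DLT-evaluable, not which late events count.

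**Illustration.** No hematologic DLT rate is documented. Let h be the chance that a patient followed to Day 42 or 56 has a late-confirmed hematologic DLT, independent between patients, with h = 0.05 / 0.10 / 0.20.
- Level cleared at 0/3 gains at least one: 1 − (1 − h)³ = 0.14 / 0.27 / 0.49.
- Level cleared at 0/3 gains two or more: 3h²(1 − h) + h³ = 0.01 / 0.03 / 0.10.
- Level cleared at 1/6 on a non-hematologic DLT moves to 2/6 or worse: 1 − (1 − h)⁵ = 0.23 / 0.41 / 0.67, over the five patients without the first DLT.

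The low end is more plausible, because each event also needs the marrow cleared to under 5% blasts. Exactly one late event after 0/3 would call only for expansion of the cohort under 4.1.1.

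**The case against.** The strongest reply is that the plan does answer the question: the observation period for escalation is one cycle, clearance is worded in terms of completing it, and a Day 42 event is simply outside. On this reading the hematologic definition still has work to do. It governs dose suspension in any cycle (6.4) and the Part 2 rule that may pause enrollment above 30%, which runs over the whole treatment period (4.1.2). The DESC reviews safety at least monthly and may act on any finding. Restricting the tally also has a rationale, since a Day 42 event reflects up to 6 weekly doses or 2 Q3W doses.

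This is a fair account of first-pass clearance, and the point accepts it. It does not remove the problem. On that reading a DLT class written into the Part 1 definition can never enter a Part 1 count on the patient's own window, and nothing says whether the MTD, whose definition has no day limit, should reflect it. DESC discretion permits the right outcome without requiring it.

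Four stronger readings are tempting and not supported.
- A reader might infer that a Day 42 event leaves the patient with no handling rule. Section 6.4 suspends dosing for a DLT in any cycle; only permanent withdrawal is unclear. The Grade 5 enrollment halt (6.5), the Grade 3 or higher non-hematologic DLT criterion and the delay after CR/CRi also limit patient risk.
- A reader might compare first-pass escalation probabilities with and without hematologic DLTs; at assumed rates of 10% for each class these are 0.730 and 0.906. That treats late events as known at first clearance, which neither the plan nor the fix does.
- A reader might infer that a dose was wrongly cleared. The documents report no late hematologic DLT.
- A reader might infer that the DLT listing will hide timing. SAP 4.8.1 does not give its columns; onset and resolution dates are collected (7.3.2.3) and all AEs are listed. What is missing is an explicit marker and a rule.

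One limit: the 3+3 schematic (Figure 2) was not available, so the absence of a rule is judged from the text.

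**Conclusion.** The concern holds. On the planned schedule a Cycle 1-onset hematologic DLT is confirmable only 21 or 35 days after the patient's window closes, so it cannot affect first-pass clearance on that window. No text adds it to the dose level's tally before further escalation or MTD naming. For patient handling, the gap is confined to whether such an event is a Cycle 1 DLT for permanent withdrawal.

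The day counts follow directly from the documents. The probabilities rest on assumed rates, independence and complete follow-up to Day 42 or 56, and they describe a re-applied tally only. Because the trial ended before escalation was complete and the SAP derives no MTD, the present effect is limited to the DLT listing and to deviation item 3. There, a patient dosed again after such an event could be counted or not.

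**What to change.** **SAP, the only change with effect now.** In the DLT listing (4.8.1), flag hematologic DLTs confirmed after Day 21. In 4.2, state whether a flagged event is a Cycle 1 DLT for item 3, and apply it accordingly. The cost is one flag and one sentence.

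**Protocol 4.1.1, 7.3.1.1 and 8.4, for any reuse of the design.** Keep the 21-day window for non-hematologic DLTs and for provisional escalation. Then:
1. Follow Cycle 1-onset Grade 3 or higher cytopenia to Day 42 or 56. Use scheduled counts, the Cycle 2 Day 19 marrow for the 6-week limb, and the existing as-clinically-indicated provision or the next scheduled marrow for the 8-week limb.
2. Add late-confirmed hematologic DLTs to that dose level's tally.
3. Have the DESC re-apply the 0/3 or at most 1/6 rule before any further escalation and before naming the MTD.
4. State whether such an event counts as a Cycle 1 DLT for permanent withdrawal.

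The costs are real but small. Some escalation decisions become provisional. Some 8-week confirmations will need an extra as-indicated marrow, since none is scheduled between about Day 43 and Day 58 and sampling is sparser after CR/CRi. Late events also mix in the effect of doses after Cycle 1, and the DESC should record this when it counts them.

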7.3.1.2 Safety Oversight by the Dose-Escalation Steering Committee

A DESC will be responsible for safety monitoring and overall supervision of the study.

Membership of the DESC will include:

- Medical Monitor(s)/Pharmacovigilance representative(s) (Sponsor and/or designee)
- Investigator(s) from each participating site
- Biostatistician(s)
- Ad hoc members (e.g., project manager, study coordinators, regulatory representatives, etc.)

In general, the DESC will make any substantial decisions regarding the conduct of the study, such as:

- Monitor the safety of the study and review its progress at monthly intervals or more frequent intervals as required.
- Determine dose levels to be administered and the MTD based on assessment of safety findings and determination of DLTs.
- Approve any amendments or administrative changes to the protocol, when required.
- Determine if it is appropriate to maintain a QW schedule, revert to a Q3W schedule, or test other dosing regimens.

Each DESC meeting and the decisions made will be documented in writing and provided to all participating DESC members and Investigators. Meeting documents may be submitted to IRBs/IECs or competent authorities according to institutional or local requirements.

The DESC will be maintained during Part 2 (expansion) of the study to continue to monitor and evaluate patient safety.

7.3.2 Adverse Events

7.3.2.1 Definitions of Adverse Events

The Investigator is responsible for reporting all AEs that are observed or reported during the study, regardless of their relationship to study drug or their clinical significance.

An AE is defined as any untoward medical occurrence in a patient enrolled into this study regardless of its causal relationship to study drug. Patients will be instructed to contact the Investigator at any time after assignment to the treatment group if any symptoms develop.

A treatment-emergent AE (TEAE) is defined as any event not present before exposure to study drug or any event already present that worsens in either intensity or frequency after exposure to study drug.

A serious adverse event (SAE) is defined as any event that results in death, is immediately life-threatening, requires inpatient hospitalization or prolongation of existing hospitalization, results in persistent or significant disability/incapacity, or is a congenital anomaly/birth defect. Hospitalization for elective procedures or for protocol compliance is not considered an SAE.

Important medical events that may not result in death, be life-threatening, or require hospitalization may be considered SAEs when, based upon appropriate medical judgment, they may jeopardize the patient or may require medical or surgical intervention to prevent 1 of the outcomes listed in this definition. Examples of such medical events include allergic bronchospasm requiring intensive treatment in an emergency room or at home, blood dyscrasias or convulsions that do not result in inpatient hospitalization, or the development of drug dependency or drug abuse.

7.3.2.2 Eliciting and Documenting Adverse Events

Adverse events will be assessed from the time the patient signs the ICF up to 84 days (12 weeks) after the last dose of study drug, or initiation of new anti-cancer treatment.

Any SAEs that occur >84 days (12 weeks) after the last dose of study drug do not need to be reported unless the Investigator considers the event to be related to study drug.

At every study visit, patients will be asked a standard non-leading question to elicit any medically-related changes in their well-being. They will also be asked if they have been hospitalized, had any accidents, used any new medications, or changed concomitant medication regimens (both prescription and over-the-counter medications).

In addition to patient observations, AEs will be documented from any data collected on the AE page of the eCRF (e.g., clinically significant changes in laboratory values, physical examination, ECG changes, etc.) or identified from review of other documents that are relevant to patient safety.

